05 APR 2019

Version 4.0

Page: 9 of 96

Frequency tables will be provided for variables measured on ordinal or nominal scales. Tables will display the number and percentage of subjects falling within a particular category.

Data will be displayed by dose level and by study medication actually received during the study parts and the corresponding visits.

Safety

Vital signs, AEs and laboratory data will be analyzed by descriptive statistics. All AEs will be tabulated according to the affected system organ class and preferred term, as coded by Medical Dictionary for Regulatory Activities (MedDRA). Separate descriptions will be delivered for the different dose levels. Special interest will be given to safety observations after application of rescue medication during the treatment phase with BAY 1093884.

Efficacy

CCI

The main focus will be the number of spontaneous bleeds requiring additional treatment.

Further details of Efficacy analysis are listed in the Statistical Analysis Plan (SAP).

Protocol amendment summary of changes

Table of main changes

Section # and name	Description of change	Brief rationale
Section 2 Synopsis Section 6.1 Inclusion criteria	Inclusion criterion 1 was modified to further specify that only subjects diagnosed with severe hemophilia, with or without inhibitors, are eligible.	Criterion updated to ensure that only hemophilic patients who are diagnosed as severe are included in the study.

Typographical, grammatical, and other minor edits are not identified.

Table of contents

Cover page of the integrated protocol.....	1
1. Title page	2
Signature of the sponsor’s medically responsible person.....	3
Signature of principal investigator.....	4
2. Synopsis.....	5
Protocol amendment summary of changes.....	10
Table of tables	14
Table of figures.....	14
List of abbreviations	15
3. Introduction.....	17
4. Study objectives.....	20
5. Study design.....	21
6. Study population	26
6.1 Inclusion criteria	26
6.2 Exclusion criteria.....	26
6.3 Withdrawal of subjects from study.....	27
6.3.1 Withdrawal.....	27
6.3.2 Replacement	28
6.4 Subject identification.....	28
7. Treatments.....	29
7.1 Treatments to be administered.....	29
7.1.1 Prophylaxis treatment with BAY 1093884	29
7.1.2 Treatment of bleeds.....	30
7.1.3 Treatment for PK/PD assessments.....	31
7.1.4 Treatment for minor and major surgery	31
7.2 Identity of study treatment.....	32
7.3 Treatment assignment.....	33
7.4 Dosage and administration	33
7.4.1 Selection of doses in the study	33

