TFPI inhibition and improvement in parameters measured with the thrombin generation assay (TGA) following weekly SC administration. For this projection, to safely evaluate the potential accumulation following multiple administration of BAY 1093884, the lower dose X will provide preliminary safety information, while is not expected to result in meaningful control of bleeding episodes over 7 days. The following Y dose is expected to provide both safety and efficacy data over the 7 days after BAY 1093884 administration. The last dose, Z, is supposed to provide additional efficacy information and safety margin, without exceeding the highest evaluated dose in the Phase 1 study.

The reason to start with 100 mg dose is that this dose is expected to result in 3-5 days of TFPI inhibition. In addition, all subjects have been exposed to 100 mg or more in the Phase 1 study, where the safety of this dose has been established. In fact, single doses of 1 mg/kg (68 - 91 mg), 3 mg/kg (213 - 270 mg) and 6 mg/kg (401 - 510 mg) have been administered in the Phase 1 study.

The rationale to include in the study both subjects treated on demand and subjects on prophylaxis who present at least 4 bleeding episodes in the previous 6 months is to ensure enrollment of subjects with high unmet need (at least 8 bleeds per year). It is well known that the annualized bleeding rate in subjects on prophylaxis is between 1 and 3 for non-inhibitor subjects (19, 20) and approximately 5 for inhibitor subjects (21).

Subjects treated on demand with previously assigned products will switch to prophylaxis with BAY 1093884, which is expected to lead to similar or lower bleeding rates. Subjects previously treated prophylactically may benefit from the study drug because of their high bleeding rate (despite frequent regular injections). In any case, any occurring bleed that will need additional control will be treated with their pre-study treatment (with already proven response) and subjects will be always allowed to continue the study or to interrupt it, based on their response to treatment and treatment satisfaction.

End of study

The end of the study as a whole will be reached as soon as the last visit of the last subject has been reached in all centers in all participating countries (EU and non-EU).

Primary completion

The primary completion event for this study is when the last subject in Cohort 3 has completed 24 weeks of treatment (end of Part B).

Communication plan

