7.1.2 Treatment of bleeds

The occurrence of bleeds of different cause, severity and site is a typical characteristic of subjects with hemophilia, being the clinical manifestation of the disease itself.

Bleeds will be classified into the following types:

- **Spontaneous:** Not attributable to any trauma or activity
- **Non-spontaneous/non-traumatic:** Not related to a trauma, but due to activity (walk, run, sport, gym, etc.)
- **Traumatic:** Related to an identified trauma

Throughout the study, all bleeds will be recorded, but only the bleeds recorded as “spontaneous” (not related to any trauma or activity) and “requiring additional treatment” will constitute the base for the efficacy evaluation.

All bleeds occurring in subjects receiving prophylactic treatment with BAY 1093884 after Visit 2 (“Start of treatment with BAY 1093884”) which require additional treatment will be treated according to the subject’s pre-study treatment as outlined in Section 8.1. Given the potential additive effect of BAY 1093884 and concomitant medication, it is recommended to treat the bleeds with the lowest approved doses of the prescribed replacement factor or bypassing agent, and repeat the dose, if additional doses will be needed, at the investigator’s judgment.

For the same reason, the investigator must carefully consider the intensity and the location of a trauma for which bleeding has not yet occurred before the preventive use of a replacement factor or a bypassing agent during treatment with BAY 1093884. Careful oversight of bleed treatment by the Investigators will ensure the patients’ safety.

If a bleed occurs on a day of the planned injection of BAY 1093884, the subject should treat the bleed with his usual medication and administer the scheduled prophylactic injection of BAY 1093884. The injection schedule with BAY 1093884 will not be affected by the treatment of bleeds.

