10.3.2 Extent of exposure

Extent of exposure to the study and reference drug (rescue medication, pre-study medication), including injection characteristics, will be summarized for all subjects receiving any amount of drug.

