10.3.5 Analysis of safety

The safety profile will be analyzed using the SAF population and safety data collected during Part A. Vital signs, AEs, and laboratory data will be analyzed by descriptive statistics, such as summary statistics and frequency tables. All AEs will be tabulated according to the affected system organ class and preferred term, as coded by the medical dictionary for regulatory affairs (MedDRA).

Further safety analyses will include all safety data available at the time when Cohort 3 will have completed Part A and Part B of the study. For each subject, safety variables will be

analyzed by study part and the respective visits and by dose actually received, both by dose cohort and by study medication actually received during the respective interval. This includes safety analyses by dose last received.

The evaluation of safety data and the version of MedDRA used for coding will be detailed in the SAP.

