10.5 Planned interim analyses

After all subjects still participating in the study have completed Part A and at least one 12-week Part B period (primary completion) of the study, all dose levels will be assessed including clinical safety, routine safety laboratory, hemostasis and thrombosis markers as per PK/PD assessment and clinical efficacy.

For safety, AEs will be assessed for all subjects per dose level. In case of comparable clinical safety, the routine lab findings will be evaluated. In case of comparable clinical and laboratory safety, thrombosis and hemostasis markers will determine safety evaluation.

For efficacy, the number of subjects without spontaneous bleeds requiring treatment in addition to BAY 1093884 will be assessed; all other efficacy variables will be assessed for the dose levels observed.

11. Data handling and quality assurance

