6.4.1 Adverse events

The investigator has to record on the respective CRF pages all adverse events occurring in the period between the signing of the informed consent form and the end of the follow-up phase. The original terms used by investigators to report AEs via the CRFs will be coded using the Medical Dictionary for Regulatory Activities (MedDRA).

For each AE, the number and percentage of subjects who experienced at least 1 occurrence of the given event will be tabulated according to the affected primary system organ class (SOC) and preferred term (PT) by dose cohort and dose actually received. A total column will be included in all safety summaries.

Frequency tables, showing an overall summary of number of subjects with drug-related AEs, SAEs and AESIs will be given, and will include the following information:

- maximum intensity for any AE,
- AE related deaths,
- AE resulting in permanent discontinuation of study drug,

- treatment emergent AE.

AEs will be considered treatment-emergent if they begin after the first administration of study drug and they do not start after more than 30 days after the last administration. Determination of whether or not an event is treatment-emergent will be derived after the missing or incomplete AE start date is imputed. Inhibitors will be defined as treatment-emergent if they develop after first study drug application. Imputation rules for missing and incomplete AE start are described in section 4.3.

The severity or intensity of an AE should be graded according to the National Cancer Institute Common Terminology Criteria for Adverse Events (NCI CTCAE) version 5.0. If no exact matching code is available in NCI CTCAE version 5.0, the following guidance should be used:

- CTCAE grade 1: Mild
- CTCAE grade 2: Moderate
- CTCAE grade 3: Severe and/or disabling AE
- CTCAE grade 4: life-threatening and/or intervention needed
- CTCAE grade 5: resulting in death (fatal)

A similar table showing overall summary information of AEs during screening will be given.

In addition, frequency tables will summarize the number of subjects with injection site reactions.

Similar to 6.2, frequency tables will summarize the number of subjects with

- any event during Part A,
- any event during each 12-week Part B period
- any event during combination of these periods.

This will also include tabulation by dose actually received.

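### The protocol singles out safety after rescue medication, but SAP 6.4 plans no summary of adverse events by rescue use, rescue product or time since rescue

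*SAP*

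**What the plan says.** The safety paragraph of the statistical plan in the protocol synopsis states: "Special interest will be given to safety observations after application of rescue medication during the treatment phase with BAY 1093884". Protocol 7.1.2 gives a reason for such interest. It opens its advice on treating bleeds with "Given the potential additive effect of BAY 1093884 and concomitant medication", and Section 8.1 repeats the point. Protocol 10.3.2 adds: "Extent of exposure to the study and reference drug (rescue medication, pre-study medication), including injection characteristics, will be summarized".

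Protocol 10.3.5 does not carry the rescue sentence forward. It plans safety by study part and visit, "both by dose cohort and by study medication actually received during the respective interval", and leaves further detail to the SAP.

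SAP 6.4.1 has each adverse event (AE) "tabulated according to the affected primary system organ class (SOC) and preferred term (PT) by dose cohort and dose actually received". It also tabulates by Part A, by each 12-week Part B period and by combinations of these. SAP 6.4.4 adds an overall summary by hemophilia type, inhibitor status and previous treatment. The 2020 addendum adds bleeding rates and individual laboratory and PK/PD plots. Nothing in SAP 6.4 or the addendum relates an AE to on-study rescue.

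Protocol 10.5 then assesses AEs for all subjects per dose level and proceeds in tiers: "In case of comparable clinical safety, the routine lab findings will be evaluated". Thrombosis and hemostasis markers decide if both earlier tiers are comparable.

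**The concern.** Safety is the primary endpoint, and thromboembolic and thrombotic microangiopathic events are adverse events of special interest (AESIs). The protocol itself raises the possibility that study drug and rescue product act together. If the SAP is followed as written, no summary of the primary endpoint will show whether events gather after rescue, or after one class of rescue product.

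Rescue use is also unlikely to be the same at every dose. Section 5 says that dose X "is not expected to result in meaningful control of bleeding episodes over 7 days". More treated bleeds, and so more rescue, may be expected at the lowest dose in Part A. A by-dose AE table would then combine the effect of the dose with the effect of the rescue that the dose leads to, and this table feeds the tiered assessment in Protocol 10.5.

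**Working it through.** The documents give no sample-size, power or event-rate figure for this point. The check is therefore mainly a comparison of passages, followed by an illustration on assumed inputs.

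**1. Commitment against planned output**

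- Safety after rescue (synopsis): no matching table, subgroup, time window or listing rule in SAP 6.4.1 to 6.4.4, which are not redacted, and none in the addendum.
- Rescue exposure (Protocol 10.3.2): the readable SAP has no extent-of-exposure section. SAP 6.2 is partly redacted, and Protocol 9.4.2 places rescue dose and number of injections under efficacy, so a summary there cannot be ruled out.
- Data: Protocol 9.4.1 has the diary record date, time, product class and number of injections for each treated bleed. AE data are in the eCRF.

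**2. Direction of the rescue gradient**

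- Part A: Section 5 suggests more rescue at X. Section 7.4.1.1 tempers this, since it does not expect dose X to be wholly without effect.
- After Part A: subjects with more than 2 treated spontaneous bleeds in Part A, or more than 1 in a later 12-week period, move to the next opened dose. By dose actually received, frequent bleeders therefore move upwards, and the gradient may weaken or reverse. SAP 6.2.1 gives this caution for efficacy; SAP 6.4 does not.

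**3. Illustration (all rates assumed)**

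Mean rescued bleeds per subject in Part A: m = annual treated-bleed rate × 84/365.25. Subject AE risk = 1 − (1 − b) × exp(−q × m), where b is the risk on study drug alone and q is the added event hazard per rescued bleed. Take b = 5%, 10% and 15% at X, Y and Z, a true Z − X difference of 10.0 points.

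- Rates 8/4/2 per year, q = 0.05. At X, m = 8 × 84/365.25 = 1.84 and risk = 1 − 0.95 × exp(−0.05 × 1.84) = 13.3%. At Z, m = 0.46 and risk = 1 − 0.85 × exp(−0.05 × 0.46) = 16.9%. Z − X = 3.6 points.
- Rates 12/4/1, q = 0.05: 17.2% at X and 16.0% at Z; Z − X = −1.3 points from unrounded values.
- Rates 8/4/2, q = 0.10: Z − X = −2.1 points.
- Equal rates 8/8/8: Z − X = 9.1 points (q = 0.05) or 8.3 points (q = 0.10).
- Any of these rates with q = 0: Z − X stays at 10.0 points.

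A material loss of the dose trend needs both conditions: rescue adds risk, and rescue use falls with dose.

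**4. What a rescue table could show**

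With 0 events, the upper exact (Clopper-Pearson) 90% limit is 31.2% for n = 8, 52.7% for n = 4 and 11.7% for n = 24. At a true risk of 10%, the chance of seeing at least one event is 57.0%, 34.4% and 92.0% respectively. Such a table describes; it cannot establish or exclude an interaction.

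**The case against.** The case on the other side is substantial.

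- *The synopsis sentence names no analysis.* It speaks of interest in observations, and Protocol 10.3.5 does not repeat it. That is so, but the sentence stands in the plan for statistical analysis, and the SAP gives it no form.
- *Individual events can be examined.* SAP 4.1 lists all data. Protocol 9.6.1.2.3 makes concomitant treatment a factor in causality assessment. Sections 9.6.1 and 9.6.1.7 send any thromboembolic or microangiopathic event to the DMC. This stands: a reader might infer that a rescue interaction could not be seen at all, and the documents do not support that. What is missing is a planned summary.
- *Existing subgroups partly stand in for rescue class,* since bleeds are generally treated with the pre-study product. They do so in part, but they carry no timing.
- *The dose comparison is not confounded in the usual sense.* A reader might infer that it is. In Part A rescue follows from dose, so it lies on the pathway from dose to AE, and the by-dose table is a valid description of dose plus resulting rescue. The study is non-randomized, with no hypothesis tests.
- *Wash-out times do not measure the risk.* A reader might multiply the Table 7-2 times by a number of bleeds and report a share of Part A spent on both drugs. Section 7.1.1 sets those times for PD evaluation, so such shares are not evidence of safety exposure.

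The SAP also cites protocol version 2.0, while version 4.0 is the one supplied. The change tables list no change to the rescue sentence, but its presence in version 2.0 is an assumption.

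**Conclusion.** The point holds as a gap between a stated safety interest and the planned output. The SAP should close it, but it does not invalidate the study. SAP 6.4 splits AEs by dose, period and baseline subgroup, and no planned table separates AEs after rescue from AEs on BAY 1093884 alone. The AE assessment in Protocol 10.5 therefore describes each dose with whatever rescue it leads to.

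The size is unknown. The illustration runs from no distortion to a reversed sign, and rests wholly on assumed bleed rates, AE risks and rescue effect. Masking of a dose trend is possible but not shown, and after Part A the direction of the rescue gradient is itself uncertain. The documents also do not show that the rescue-exposure summary has been dropped, because part of SAP 6.2 is redacted.

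**What to change.** In SAP 6.4.1:

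1. Flag each treatment-emergent AE, SAE and AESI by whether its onset falls within a pre-defined, product-specific window after the last non-study hemostatic infusion. Keep standard and extended half-life products separate. If the Table 7-2 times serve as the window, state that this is an assumption.
2. Show events and subject-days inside and outside the window by dose actually received, with a listing by rescue class.
3. Present this and the rescue-exposure summary of Protocol 10.3.2 beside the AE table used for the Protocol 10.5 assessment.
4. Repeat the SAP 6.2.1 caution that dose after Part A depends on post-baseline events.
5. Say how events with an imputed onset are handled. SAP 4.3 sets a missing start day to the 15th of the month, which is too coarse for a window of days.

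The cost is SAP wording, programming and a few outputs. No new data appear to be needed: the diary holds rescue timing and class, the CRF holds products used for minor surgery (Protocol 9.4.3), and the medication history (Protocol 9.3.4) gives trade names if the diary class does not separate extended half-life products. The drawback is very small cells with 8 subjects per cohort, so the output should be labelled descriptive.

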4.3 Handling of Missing Data

All missing or partial data will be presented in the subject data listing as they are recorded on the Case Report Form (CRF).

General rules

When appropriate, the following rules will be implemented so as not to exclude subjects from statistical analyses due to missing or incomplete data:

- **Efficacy Variables**

If the details of a bleed are missing (e.g., type of bleed spontaneous, non-spontaneous/non-traumatic or traumatic), the bleed will be counted for all categories of bleeds, but not for the corresponding subgroup of bleeds.

Each subject's bleeding period start date will be needed to allocate the bleedings to the respective period. If dates for bleeds and injections of rescue medication are both missing then these bleeds cannot be counted. If the bleed date is missing, but the injection date is available, injection date will be used.

- **AE Variables**

For the purpose of treatment-emergent flags, missing AE start day will be imputed as the 15th of the month. However, if the AE start day is missing, but the AE starts during the same month or on the same day as the first dose, but the AE start time is missing, the AE start day (and time in the second case) will be taken from first dose start day (and time). If both day and month of AE start date are missing, day and month will be imputed as the date of the first dose.

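### The SAP imputes an AE on the first-dose day with no start time to the first dose itself, then requires onset after that dose, so read literally it is not treatment-emergent

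*SAP*

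**What the plan says.** SAP 6.4.1 sets the start criterion: "AEs will be considered treatment-emergent if they begin after the first administration of study drug". The event must also start no more than 30 days after the last administration. On the order of steps, the same section says: "Determination of whether or not an event is treatment-emergent will be derived after the missing or incomplete AE start date is imputed". The imputed value therefore decides the flag whenever the onset is incomplete.

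SAP 4.3 gives the imputation rules and ties them expressly to the treatment-emergent flag:

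- Default: "missing AE start day will be imputed as the 15th of the month".
- Exception, for a missing day in the first-dose month (first case) or a missing time on the first-dose day (second case). The trigger reads "the AE starts during the same month or on the same day as the first dose, but the AE start time is missing", and the value is given as "the AE start day (and time in the second case) will be taken from first dose start day (and time" (closing bracket omitted). A time is imputed only in the second case.
- Year only: "If both day and month of AE start date are missing, day and month will be imputed as the date of the first dose". No time is imputed.

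Neither section says what happens when the imputed onset equals the first dose. In SAP 6.4.1 the flag appears as one entry, "treatment emergent AE", in the list of contents of the overall AE summary.

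**The concern.** Imputing an uncertain onset to the first dose makes sense if the aim is to count the event as on treatment when it cannot be shown to precede treatment. SAP 4.3 introduces its rules as a way to avoid losing subjects from analyses through incomplete data. A start criterion that requires onset after the first dose has the opposite effect, because the imputed onset is never later than the dose it was copied from.

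Safety is the primary objective, and the first injection is an obvious moment to look for reactions. A flag that drops events from that day because a clock time is missing would understate the treatment-emergent count. It would do so because of the wording of a rule and not because of anything in the data.

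**Working it through.** The plan states no figure to reproduce, so the check applies the rules literally.

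**Inputs.** Imputation rules from SAP 4.3; start criterion, 30-day limit and order of steps from SAP 6.4.1; 8 subjects per cohort from SAP 9.1. Assumed for illustration: first dose on 20 Sep 2018 at 10:30.

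**Step 1: start criterion.** The test is onset > first dose as written, and onset ≥ first dose as the alternative. Where SAP 4.3 imputes no time, three conventions are possible: compare dates only, set the time to 00:00, or set it to 23:59. Entries show whether the start criterion is met, in that order.

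| Known part of onset | Imputed onset | As written (>) | Alternative (≥) |
|---|---|---|---|
| 20 Sep 2018, no time | 20 Sep 2018, 10:30 | no / no / no | yes / yes / yes |
| Sep 2018, no day | 20 Sep 2018, no time | no / no / yes | yes / no / yes |
| 2018 only | 20 Sep 2018, no time | no / no / yes | yes / no / yes |
| Oct 2018, no day | 15 Oct 2018 | yes / yes / yes | yes / yes / yes |
| Aug 2018, no day | 15 Aug 2018 | no / no / no | no / no / no |
| 2019 only | 20 Sep 2019 | yes / yes / yes | yes / yes / yes |

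The first row fails under every convention, because 10:30 is not after 10:30. Rows two and three pass only under the 23:59 convention, which the SAP does not state. The last three rows involve no tie. Changing > to ≥ repairs the first row fully. It repairs rows two and three on a date comparison but not under 00:00, so a tie rule is needed as well.

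**Step 2: end of the window, year-only onset.** Assume a first dose on 12 Nov 2018 and 24 weekly doses, the last on 12 Nov 2018 + 23 weeks = 22 Apr 2019. The window closes on 22 Apr 2019 + 30 days = 22 May 2019. An AE dated only 2019 is imputed to 12 Nov 2019 and excluded, although the subject was on drug from January to April 2019.

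**Step 3: end of the window, fixed 15th.** Assume a last dose on 10 April. The window closes on 10 April + 30 days = 10 May. An AE dated only May is imputed to 15 May and excluded, although 1 to 10 May lies inside the window.

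**Step 4: size.** SAP 6.4.1 counts subjects with at least one event. One subject in a cohort of 8 is 1/8 = 12.5 percentage points, provided that subject has no other event that qualifies for the same row.

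**The case against.** The strongest reply is that the reach is narrow. The primary variables in SAP 6.4 and protocol 10.3 are not worded as restricted to treatment-emergent events. Nor are the SOC/PT tables, the injection site reaction table or the by-period tables in SAP 6.4.1. Hypersensitivity is an AESI and injection site reactions have their own table, so both are reported whatever the flag says. This stands, and it sets the size of the point.

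The reply also holds that a programmer would see the inclusive intent of SAP 4.3 and code onset on or after the dose. That is plausible, but the code would then depart from the text. The end-of-window examples are edge cases: protocol section 5 allows further Part B periods and an extension, and for a subject still dosed in autumn 2019 an imputed 12 Nov 2019 would be counted. The fixed 15th can also err the other way, by counting an onset that truly fell after the window. Both remarks are correct.

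Three stronger readings are tempting, and the documents do not support them:

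- A reader might infer that these events would be reported as screening events, since SAP 6.4.1 adds: "A similar table showing overall summary information of AEs during screening will be given". But the SAP does not define that table as everything that fails the flag.
- A reader might infer that first-injection reactions are the events most likely to lack a time. No missing-time rate is given. Supervised first injections with 30-60 minutes of observation (protocol 7.1.1), or about 1 h (protocol 9.6.1.4), suggest that their timing should be well recorded.
- A reader might infer that every incomplete onset is lost. The table above shows otherwise.

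**Conclusion.** The two SAP sections contradict each other on one exact case: an AE on the first-dose day with no start time is imputed to the first dose and then, read literally, excluded by the start criterion. The two date-only cases fail as well under a date-level or 00:00 comparison, because there is no tie rule. The year-only and fixed-15th rules can misplace an onset near the end of the 30-day window, but only in edge cases.

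What is affected is the treatment-emergent item of the overall AE summary. The documents do not support a claim that the primary safety result is understated. The number of affected AEs is unknown and may be zero; the 12.5-point figure is the effect of one reclassified subject in a cohort of 8, under the condition given with it. The conclusion assumes that the flag is programmed as the SAP is written, and the dates used are illustrative.

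**What to change.** - **SAP 6.4.1:** define treatment-emergent as onset on or after the first administration and no more than 30 days after the last. State that when only the date is available and it equals the first-dose date, the event counts as treatment-emergent.
- **SAP 4.3:** for the flag, count any partial onset as treatment-emergent unless its known parts show that it began before the first dose or more than 30 days after the last dose. This replaces the fixed 15th and the first-dose day and month rule. It also covers the date-only ties and the end-of-window cases without relying on a default time.
- **Programming:** check how the flag was coded, and bring text and code into line.

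The cost is a small edit to two SAP sections and the derivation code. Slightly more AEs will be counted as treatment-emergent, including some that truly began outside the window. For a safety summary that is the conservative direction.
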